7.1 Treatment of missing values and outliers

The missing values will not be filled. The handling of outliers will be discussed and decided at the data review meeting.

7.2 Processing of data rounding

Minimum, maximum, mean, median, quartile, standard deviation, confidence interval reserve at least four significant digits or two decimals; percentages reserve two decimals. In the process of calculation, the original data is used to calculate, and only when the final data is presented, it is rounded.

7.3 Handling of other abnormal data

If the format of the security data is inconsistent (such as date/time, etc.), it is uniformly intercepted upward to the same format during processing, and downward filling is not considered.

If there is no clinical judgment of the safety index, the statistician shall not evaluate the data during the analysis, and compare it with the normal range and classify it into low, medium and high levels.

If there is a vacancy, according to the statistical table specification, the cross table or the change table before and after medication should be indicated by "missing" or "N/A". However, in the schedule, the data shown are all raw data, and no other processing of the data is considered.

The statistical time of adverse events and combined use of drugs will be from entering the group to the end of the trial. Adverse events and combined use of drugs during the screening period and at other times will not be reflected in the report and will only be listed in the attached table.

8 Statistical methods

8.1 General principles

In this study, the statistical analysis will be completed by SAS 9.4 ®software, and part of the statistical charts will be completed by SPICE 6. The related database is exported and saved in SAS XPORT format.

The statistical analysis plan is formulated by biostatisticians and the principal

investigator according to the protocol, and the final document is refined and formed before the data is locked.

- Continuous variables will be described by mean, standard deviation, median, quartile, minimum, maximum, and coefficient of variation.
- The categorical and ranked data will be described by frequency and percentage.
- The continuous variables will be analyzed by analysis of variance. When the test level is $\alpha=0.05$ and $P\leq 0.05$, the difference will be considered to be statistically significant, and the pairwise comparison will be made by SNK method.
- Chi-square test will be used to classify the categorical variables, and the difference is considered to be statistically significant when the test level is $\alpha=0.05$ and $P\leq 0.05$. the chi-square partition method will be used for pairwise comparison, and the Bonferroni method will be used to correct α , $\alpha' = \alpha/\text{comparison times}$.
- The rank sum test will be used for the data of unknown or non-normal distribution, and the difference is considered to be statistically significant when the test level is $\alpha=0.05$ ($P\leq 0.05$). Pairwise comparison using Bonferroni method to correct α , $\alpha' = \alpha/\text{comparison times}$

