3.3 Sample size

This phase 2 trial is launched before we obtaining the immunogenicity data from the phase 1 trial. Therefore, the sample size of is not calculated, but determined based on expert experiences and the minimum sample size requirement in the technical guidelines for vaccine clinical trials issued by National Medical Products Administration, China. The final sample size is 250 in the middle dose group, 125 in

the low dose group and 125 in the placebo group, with a total sample size of 500.

The antibodies of all participants are measured by ELISA at day 0, day 14, day 28 and month 6, and the antibodies of participants are measured by live SARS-CoV-2 or pseudovirus neutralization test at day 0, day 28, and month 6.

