3.4 Randomization and blinding

3.4.1 Randomization and grouping

In this study, randomization and blindness will be achieved by blinding the investigational vaccines. Qualified test vaccines and placebos will be provided by the sponsor, and then be blinded by a third party. SAS software is used to generate random codes by block randomization, and the test vaccine and placebo will be randomly assigned to serial numbers (the vaccine for each participant has a unique serial number). Participants will be randomly divided into the middle dose group, low dose group, and placebo group at a ratio of 2:1:1.

The investigator assigned the random numbers in order of the eligible participants arrived at the place where study number assigned, and filled the screening number and initials into the corresponding column of the random number assignment table, the corresponding number is the study number. In order to control the selection bias of age and gender, the age and gender distribution among the groups should be balanced as much as possible.

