5.1 Primary endpoint

5.1.1 Safety endpoint

- Occurrence of adverse reactions (AR) within 14 days after vaccination.

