6.1 Data set for safety evaluation

All participants who received vaccination after randomization should be included in the safety evaluation. Data of the participants who violate the protocol should not be excluded.

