8.6 Safety Analysis

- Adverse reactions for 0-14 days after vaccination.
 - Statistics on the number of participants, episode and percentage of participants of vaccine-related adverse events occurred 0-14 days after vaccination.
 - Statistics on the number of participants, episode and percentage of participants of vaccine-related adverse events occurred 0-14 days after vaccination according to the severity,

symptoms and time of occurrence (within 30min after vaccination).

- Chi-square test or Fisher's exact test is used for comparison between groups.
- Adverse events for 0-14 days after vaccination
 - Statistics on the number of participants, episode and percentage of participants of adverse events occurred 0-14 days after vaccination.
 - Statistics on the number of participants, episode and percentage of participants of adverse events occurred 0-14 days after vaccination according to severity, correlation and symptoms.
 - Chi-square test or Fisher's exact test is used for comparison between groups.
- Adverse events for 0-28 days after vaccination
 - Statistics on the number of participants, episode and percentage of participants of adverse events occurred 0-28 days after vaccination.
 - Statistics on the number of participants, episode and percentage of participants of adverse events occurred 0-28 days after vaccination according to severity, correlation and symptoms.
 - Chi-square test or Fisher's exact test is used for comparison between groups.
- Serious adverse events for 0-28 days after vaccination.
 - Statistics on the number of participants, episode and percentage of participants of serious adverse events occurred 0-28 days after vaccination.
 - Statistics on the number of participants, episode and percentage of participants of adverse events occurred 0-28 days after vaccination according to severity, correlation and symptoms.
 - Chi-square test or Fisher's exact test is used for comparison between groups.
- Serious adverse events within 6 months after vaccination.
 - Statistics on the number of participants, episode and percentage of participants of serious adverse events occurred within 6 months after vaccination.
 - Statistics on the number of participants, episode and percentage of participants of adverse events occurred within 6 months after vaccination according to severity, correlation and symptoms.
 - Chi-square test or Fisher's exact test is used for comparison between groups.

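### Bonferroni on pairwise categorical and rank-sum tests is valid but needlessly conservative with three groups; an explicit three-group gate would allow each pair to be tested at 0.05

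*SAP*

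**What the plan says.** The trial has exactly three groups. SAP 3.3 states "The final sample size is 250 in the middle dose group, 125 in" each of the low-dose and placebo groups, 500 in total, and 3.4.1 gives the matching 2:1:1 allocation.

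SAP 8.1 sets three rules:

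- **Categorical variables:** a chi-square test at 0.05, then "the chi-square partition method will be used for pairwise comparison, and the Bonferroni method will be used to correct" alpha, which is divided by the number of comparisons. That number is not given.
- **Rank-sum variables:** an overall test at 0.05, with the same Bonferroni division for pairs.
- **Variables analysed by ANOVA:** "the pairwise comparison will be made by SNK method", with no Bonferroni step.

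No sentence in 8.1 says that pairs are tested only after a significant overall result.

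The primary safety endpoint (5.1.1) is "Occurrence of adverse reactions (AR) within 14 days after vaccination". For it, 8.6 says only "Chi-square test or Fisher's exact test is used for comparison between groups" and names no pairwise method. In 8.7, pairwise chi-square or Fisher tests are listed for seroconversion and positive rates without mention of a correction, while Bonferroni is repeated for the Wilcoxon comparisons of ELISpot IFN-gamma levels.

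**The concern.** If 8.1 is read in sentence order, a pairwise categorical difference must pass two hurdles: a three-group test at 0.05 and then a pairwise test at 0.05/3 = 0.0167. With three groups, the first hurdle can already supply the familywise protection that the second is meant to give.

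What is at stake is power for pairwise contrasts, above all middle against low dose, where the difference is likely to be smaller than against placebo. The sample size was not derived from a power calculation (3.3), so no planned reserve absorbs the loss. For adverse reactions, a stricter threshold makes it more likely that a real but modest excess is reported as not significant. The plan also treats its endpoints unevenly: ANOVA variables get a stepwise procedure, categorical and rank-sum variables a stricter one, and no reason is given.

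**Working it through.** **Inputs.** Group sizes are 250/125/125 (3.3) and the overall level is 0.05 (8.1). The safety set is all vaccinated participants (6.1), so group sizes are taken as randomised. Three comparisons (alpha' = 0.0167) are assumed, with two (0.025) as the alternative. All reaction rates are assumptions. The SAP states no power, so there is no figure to reproduce.

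**Step 1: error control by closure.** The pairwise nulls are M = L, M = P and L = P. If any two are true, all three groups are equal. The only intersection hypothesis that closed testing needs is therefore the global null, which the three-group test addresses. Once that test is significant at 0.05, each pair may be tested at 0.05. The argument carries over to rank tests when the null is identical distributions.

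**Step 2: check by simulation.** Binary outcome, 250/125/125, 400,000 runs per scenario:

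| Procedure | All three equal | Two groups equal |
|---|---|---|
| Gate, then pairs at 0.05 | 0.047–0.051 | 0.044–0.053 |
| Gate, then Bonferroni | 0.036–0.043 | about 0.017 |
| No gate, pairs at 0.05 | about 0.12 | 0.049–0.053 |

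The small excess over 0.05 is discreteness of the chi-square test. The figure of 0.017 arises because one true null remains and is tested at 0.05/3. The last row shows that the gate is essential if Bonferroni is dropped.

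**Step 3: power for one pair.** Normal approximation:

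power = Φ[(|p1 − p2| − z·SE0)/SE1], with SE0 = √[p̄(1 − p̄)(1/n1 + 1/n2)] and SE1 = √[p1(1 − p1)/n1 + p2(1 − p2)/n2].

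Example, middle 75% against low 60%:

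- p̄ = (187.5 + 75)/375 = 0.70
- SE0 = √(0.21 × 0.012) = 0.0502
- SE1 = √(0.00075 + 0.00192) = 0.0517
- At 0.05 (z = 1.960): Φ(1.00) = 0.841
- At 0.0167 (z = 2.394): Φ(0.58) = 0.718

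Other assumed rates (losses taken from unrounded powers):

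| Low → middle | Power at 0.05 | Power at 0.0167 | Loss (points) |
|---|---|---|---|
| 3% → 10% | 0.702 | 0.504 | 19.8 |
| 20% → 30% | 0.544 | 0.364 | 17.9 |
| 40% → 45% | 0.148 | 0.069 | 7.9 |
| 40% → 50% | 0.448 | 0.284 | 16.3 |
| 40% → 60% | 0.958 | 0.901 | 5.7 |
| 60% → 75% | 0.841 | 0.718 | 12.3 |
| 70% → 90% | 0.996 | 0.988 | 0.8 |

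For low-dose rates of 10–70% the largest loss is 16.5 to 18.8 points. Losses of 20 or slightly more occur only at low-dose rates of about 3% or less. With two comparisons the loss is at most about 12 points.

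**Step 4: allow for what the gate costs.** Step 3 ignores the gate, which costs power when placebo is close to the low dose. With placebo equal to low dose, the gain from dropping Bonferroni shrinks to 3–12 points: for low and placebo 40% and middle 50%, gated power is 0.383 at 0.05 and 0.287 with Bonferroni.

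The gated 0.05 rule still beats Bonferroni used without any gate: 0.383 against 0.290 in that scenario, and 0.63 against 0.53 for middle, low and placebo rates of 10%, 3% and 5%. The reason is that the thresholds nearly coincide. The gate needs a chi-square of −2 ln(0.05) = 5.99 on 2 df; Bonferroni needs 2.394² = 5.73 on 1 df. The three-group statistic is usually at least about as large as a pairwise one, so the gate seldom blocks a pair that Bonferroni would pass. This comparison was made for a divisor of three only.

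**The case against.** **Bonferroni is a valid, pre-specified adjustment.** This stands. A reader might infer that 8.1 contains a statistical error. It does not; the point is one of efficiency.

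**The gate is not in the text.** This also stands. A reader might infer that the correction contributes nothing to error control. That is true only if the three-group test is binding. As written, the overall and pairwise rules are separate statements, and without a gate Bonferroni is what keeps familywise error from about 12%. The objection does not defeat the change, because the change writes the gate in.

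**The link to the primary safety endpoint is indirect.** Correct: 8.6 names no pairwise test, so the correction reaches adverse reactions only as a general rule from 8.1.

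**Continuous data are not all spared.** A reader might infer that every continuous endpoint escapes the penalty. IFN-gamma levels, compared by rank-sum tests, carry it in 8.7. Only ANOVA variables avoid it, and SNK is itself a multiplicity procedure, so the plan does not set two different nominal error rates.

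**A gate can also hide a safety difference.** Partly right: at 10%, 3% and 5% the gate lowers uncorrected middle-against-low power from 72% to 63%. Bonferroni gives 53% there. In addition, 8.6 tabulates numbers and percentages of participants with events, so an excess remains visible whatever the P value. Interval estimates that do not depend on the gate are the better answer for safety.

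**Conclusion.** The correction is valid but more conservative than a three-group trial requires. With an explicit gate at 0.05, pairwise tests at 0.05 hold familywise error at about 5% for each endpoint. Multiplicity across endpoints, assays and visits is untouched by either rule.

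A reader might take one fixed power loss from this, such as 12 to 20 points. The documents do not support that, because they give neither reaction rates nor the number of comparisons. What can be said is conditional: with three comparisons the loss runs from about 0 to about 20 points, typically 5 to 18 for modest differences and near zero for large ones; with two comparisons it is at most about 12. Contrasts with placebo lose little when the vaccine effect on reactions is large. This is a cheap improvement, not a defect that invalidates the analysis.

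**What to change.** In SAP 8.1, state that pairwise chi-square or Fisher tests and pairwise Wilcoxon tests are carried out only if the corresponding three-group test has P ≤ 0.05, each then at 0.05. Delete the division of alpha in the same edit; the two changes must not be separated. Bring the ELISpot Wilcoxon rule in 8.7 into line, and say in 8.6 whether the pairwise rule applies to safety endpoints.

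For adverse reactions, adverse events and serious adverse events, add pairwise risk differences with 95% CIs, reported whatever the three-group result.

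If the sponsor prefers to keep Bonferroni, 8.1 should at least give the number of comparisons and say whether the overall test is a gate.

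The cost is a few sentences, with no loss of error control per endpoint. The drawback is that no pairwise difference can be declared when the three-group test is not significant; compared with Bonferroni over three comparisons, this rarely matters.

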8.2 Analysis of participants' enrollment

- Statistics on the number of selected, completed and uncompleted participants.
- Statistics on the number of participants included in each dataset and a detailed list of datasets.
- Statistics on the number of participants who deviate/violate the protocol and the reasons.
- Draw the flow chart of participant distribution.
- The list shows the participants who did not complete the trial and the reasons for dropout.

8.3 Demographic data and Baseline analysis

Descriptive statistical demographic data and other baseline values:

- The participants' age, sex, height, weight and BMI are statistically described.
- To make a statistical description of the combined diseases of the participants.
- Descriptive statistics of participants' baseline vital signs, pregnancy test, etc.
- The measurement data calculates the number, mean, standard deviation, median, quartile, minimum and maximum values.
- The frequency and constituent ratio of counting data are calculated.

8.4 Compliance Analysis

- The compliance of blood collection of participants will be counted.
- List the detail of the vaccination, safety observation and blood collection of the participants.

8.5 Analysis of combined drugs/combined vaccines

- Describe the occurrence of combined drug use and calculate the percentage of participants with combined drug use.
- The combined drugs are classified by WHO ATC code, the number, episode and percentage of combined drug use are described according to the coded system and standard name.
- Describe the occurrence of the combined vaccine and calculate the percentage of participants receiving combined vaccine.
- The drugs list describes in detail the usage, dosage, using time, etc., of the combined drug/combined vaccine.

8.6 Safety Analysis

- Adverse reactions for 0-14 days after vaccination.
 - Statistics on the number of participants, episode and percentage of participants of vaccine-related adverse events occurred 0-14 days after vaccination.
 - Statistics on the number of participants, episode and percentage of participants of vaccine-related adverse events occurred 0-14 days after vaccination according to the severity,

symptoms and time of occurrence (within 30min after vaccination).

- Chi-square test or Fisher's exact test is used for comparison between groups.
- Adverse events for 0-14 days after vaccination
 - Statistics on the number of participants, episode and percentage of participants of adverse events occurred 0-14 days after vaccination.
 - Statistics on the number of participants, episode and percentage of participants of adverse events occurred 0-14 days after vaccination according to severity, correlation and symptoms.
 - Chi-square test or Fisher's exact test is used for comparison between groups.
- Adverse events for 0-28 days after vaccination
 - Statistics on the number of participants, episode and percentage of participants of adverse events occurred 0-28 days after vaccination.
 - Statistics on the number of participants, episode and percentage of participants of adverse events occurred 0-28 days after vaccination according to severity, correlation and symptoms.
 - Chi-square test or Fisher's exact test is used for comparison between groups.
- Serious adverse events for 0-28 days after vaccination.
 - Statistics on the number of participants, episode and percentage of participants of serious adverse events occurred 0-28 days after vaccination.
 - Statistics on the number of participants, episode and percentage of participants of adverse events occurred 0-28 days after vaccination according to severity, correlation and symptoms.
 - Chi-square test or Fisher's exact test is used for comparison between groups.
- Serious adverse events within 6 months after vaccination.
 - Statistics on the number of participants, episode and percentage of participants of serious adverse events occurred within 6 months after vaccination.
 - Statistics on the number of participants, episode and percentage of participants of adverse events occurred within 6 months after vaccination according to severity, correlation and symptoms.
 - Chi-square test or Fisher's exact test is used for comparison between groups.

8.7 Immunogenicity Analysis

- Specific antibody against S protein of SARS-CoV-2 (ELISA method) (day 0, day14, day 28, and month 6).
 - The geometric mean titer (GMT) of each visit in each group is described by numbers, geometric mean, standard deviation, median, quartile, maximum and minimum, etc.
 - Count the conversion rate of each group, expressed by the number and percentage, and calculate the 95%CI of the conversion rate.
 - The geometric mean fold increase (GMI) of each visit in each group is described by effective numbers, geometric mean, standard deviation, median, quartile, maximum and minimum, etc.
 - Stratification analysis is carried out according to the level of Ad5 antibody before immunization ($Ad5 > 200$, $Ad5 \leq 200$).
 - The continuous index is compared by analysis of variance between groups, and the pairwise comparison between groups is carried out by SNK method.
 - Chi-square test or Fisher's exact test is used to compare the classification index between groups, and chi-square segmentation/Fisher's exact test is used for pairwise comparison between groups.
 - Draw a reverse cumulative distribution map

- Specific neutralizing antibody against SARS-CoV-2 (neutralization test with live SARS-CoV-2 and its pseudovirus) (day 0, day 28, and month 6).
 - The geometric mean titer (GMT) of each visit in each group is described by numbers, geometric mean, standard deviation, median, quartile, maximum and minimum, etc.
 - Count the conversion rate of each group, expressed by the number and percentage, and calculate the 95%CI of the conversion rate.
 - The geometric mean fold increase (GMI) of each visit in each group is described by effective numbers, geometric mean, standard deviation, median, quartile, maximum and minimum, etc.
 - Stratification analysis is carried out according to the level of Ad5 antibody

before immunization ($Ad5 > 200$, $Ad5 \leq 200$).

- The continuous index is compared by analysis of variance between groups, and the pairwise comparison between groups is carried out by SNK method.
 - Chi-square test or Fisher's exact test is used to compare the classification index between groups, and chi-square segmentation/Fisher's exact test is used for pairwise comparison between groups.
 - Draw a reverse cumulative distribution map
- Specific neutralizing antibody of Ad5 (day 0, day 28, and month 6).
- The geometric mean titer (GMT) of each visit in each group is described by numbers, geometric mean, standard deviation, median, quartile, maximum and minimum, etc.
 - Count the positive rate of Ad5 in each group, expressed by the number and percentage, and calculate the 95%CI of the positive rate.
 - The geometric mean fold increase (GMI) of each visit in each group is described by effective numbers, geometric mean, standard deviation, median, quartile, maximum and minimum, etc.
 - Stratification analysis is carried out according to the level of Ad5 antibody before immunization ($Ad5 > 200$, $Ad5 \leq 200$).
 - The continuous index is compared by analysis of variance between groups, and the pairwise comparison between groups is carried out by SNK method.
 - Chi-square test or Fisher's exact test is used to compare the classification index between groups, and chi-square segmentation/Fisher's exact test is used for pairwise comparison between groups.
 - Draw a reverse cumulative distribution map
- Detection of IFN- γ stimulated by S protein overlapping peptide library by ELISpot (day 28).
- The ELISpot of each group and each visit is used to detect the level of IFN- γ

stimulated by S protein overlapping peptide library, which is described by numbers, mean, standard deviation, median, quartile, maximum, minimum, and 95%CI, etc.

- Count the positive rate of ELISpot of each group and each visit, expressed by the number and percentage, and calculate the 95%CI of the positive rate.
- Stratification analysis is carried out according to the level of Ad5 antibody before immunization ($Ad5 > 200$, $Ad5 \leq 200$).
- Rank sum test is used for comparison of IFN- γ levels among groups, Wilcoxon rank sum test is used for pair comparison between groups adjusted by Bonferroni method.
- Chi-square test or Fisher's exact test is used to compare the positive rate between groups, and chi-square segmentation/Fisher's exact test is used for pairwise comparison between groups.
- Draw a bar chart of the level and positive rate of cellular response.
- Make statistics according to the positive and negative test results provided by the testing organization

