3.5 Inclusion and exclusion criteria

Inclusion criteria

- Aged 18 years and over.
- Able to understand the content of informed consent and willing to sign the informed consent.
- Able and willing to comply with the requirements of the clinical trial protocol and able to complete a 6-month study follow-up.
- Negative in HIV diagnostic blood test.
- Axillary temperature $\leq 37.0^{\circ}\text{C}$.
- Negative serum IgM and IgG to the SARS-CoV-2.
- A body mass index (BMI) are between 18.5 and 30.0.

- General good health as established by medical history and physical examination.

Exclusion criteria

- Family history of seizure, epilepsy, brain or mental disease
- Participant that has an allergic history to any ingredient of vaccines
- Woman who is pregnant, breast-feeding or positive in pregnancy test on day of enrollment, or is planning to be pregnant during the next 6 months
- Any acute fever disease or infections
- Have a medical history of SARS infection
- Have serious cardiovascular diseases, such as arrhythmia, conduction block, myocardial infarction, severe hypertension and not well-controlled
- Major chronic illness, such as asthma, diabetes, or thyroid disease, and not well-controlled
- Hereditary angioneurotic edema or acquired angioneurotic edema
- Urticaria in last one year
- Asplenia or functional asplenia
- Platelet disorder or other bleeding disorder may cause injection contraindication
- Faint at the sight of blood or needles.
- Prior administration of immunodepressant or corticosteroids, antianaphylaxis treatment, cytotoxic treatment in last 6 months
- Prior administration of blood products in last 4 months
- Prior administration of other research medicines in last 1 month
- Prior administration of attenuated vaccine in last 1 month
- Prior administration of subunit vaccine or inactivated vaccine in last 14 days
- Being treated for tuberculosis
- Any condition that in the opinion of the investigators may interfere with the evaluation of study objectives

4 Investigational vaccine and inoculation Method

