5.1.2 Immunogenicity endpoint

- Geometric mean titer (GMT) of antigen-specific antibody at day 28 after vaccination measured by ELISA.
- Geometric mean titer (GMT) of specific neutralizing antibody against SARS-CoV-2 at day 28 after immunization measured by live SARS-CoV-2 and pseudovirus neutralization test.

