5.2.2 Immunogenicity endpoint

- Geometric mean titer (GMT) of antigen-specific antibody at day 14, and month 6 measured by ELISA.

- Geometric mean titer (GMT) of specific neutralizing antibody against SARS-CoV-2 at month 6 after immunization measured by live SARS-CoV-2 and pseudovirus neutralization test.
- Seroconversion rate of antigen-specific antibody at day 14, day 28, and month 6 measured by ELISA.
- Geometric mean fold increase (GMI) of antigen-specific antibody at day 14, day 28, and month 6 measured by ELISA.
- Seroconversion rate of specific neutralizing antibody against SARS-CoV-2 at day 28, and month 6 measured by live SARS-CoV-2 and pseudovirus neutralization test.
- Geometric mean fold increase (GMI) of specific neutralizing antibody against SARS-CoV-2 at day 28, and month 6 measured by live SARS-CoV-2 and pseudovirus neutralization test.
- Geometric mean titer (GMT) of neutralizing antibody against Ad5 at day 28, and month 6.
- Geometric mean fold increase (GMI) of neutralizing antibody against Ad5 at day 28, and month 6
- The positive rate and level of IFN- γ stimulated by S protein overlapping peptide library at day 28 measured by ELISpot.

For uncertain values: when calculating GMT, GMI and seroconversion of antibodies, if the antibody level is below the initial detection limit, half of the initial value will be used; if the antibody level is greater than the detection limit, the maximum dilution will be used.

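### The three-arm ANOVA with SNK for day-28 SARS-CoV-2 titres lets a near-constant placebo arm shrink the error term for middle versus low dose, and gives no GMT ratio or interval

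*SAP*

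**What the plan says.** SAP section 5.1.2 makes the day-28 titre a primary endpoint: "Geometric mean titer (GMT) of antigen-specific antibody at day 28 after vaccination measured by ELISA", together with the day-28 neutralizing GMT. In section 8.7 the only between-group test for these titres is: "The continuous index is compared by analysis of variance between groups, and the pairwise comparison between groups is carried out by SNK method". Section 8.1 sets the test level at 0.05.

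Three other provisions bear on the spread in each arm:

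- Section 3.5 admits only people with "Negative serum IgM and IgG to the SARS-CoV-2".
- Section 5.2.2 fixes undetectable results: "if the antibody level is below the initial detection limit, half of the initial value will be used".
- Section 3.3 gives the arm sizes: "The final sample size is 250 in the middle dose group". Low dose and placebo have half as many, 125 each, which makes 500 overall.

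For GMT and GMI, section 8.7 lists descriptive statistics without a confidence interval. It does ask for a 95% CI for conversion rates, positive rates and the IFN-gamma level. Nowhere does the SAP name a log transformation for the ANOVA, an unequal-variance method, a comparison restricted to the two doses, or a GMT ratio.

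**The concern.** ANOVA assumes one common variance and estimates it from all three arms. Here the plan's own rules work against that assumption. Unvaccinated seronegative participants should mostly stay at or near the assay floor, where they all receive the same value. Their small variance is averaged into the error term used to compare the two doses, although placebo says nothing about how variable vaccinated titres are.

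SNK does not protect against this. It works down from the widest range, so placebo is separated first. Middle versus low dose is then tested as two adjacent means at the unadjusted 0.05 cut-off, with the reduced error term.

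At stake is the error rate of the dose comparison and how it is reported. SNK yields a significant or non-significant result but no interval. Section 3.3 says the sample size was not calculated, so a ratio with its interval is the natural way for a reader to see how precisely the doses were compared.

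**Working it through.** The SAP states no SD, power or sample-size calculation, so there is no figure of its own to reproduce except the nominal 5%.

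**Inputs from the SAP.** Arms of 250 (middle), 125 (low) and 125 (placebo); alpha 0.05. Error degrees of freedom: 500 − 3 = 497, of which placebo supplies 124.

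**Assumed inputs.** No true difference between doses; both dose arms well above placebo; SDs (s_m, s_l, s_p) on the log10 scale, as shown below.

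**Formulas.**
- MSE = (249 s_m² + 124 s_l² + 124 s_p²) / 497
- True SE² = s_m²/250 + s_l²/125
- Critical value for two adjacent means: q(2, 497)/√2 = 1.965, the same as an ordinary t-test
- SE used = √[MSE × (1/250 + 1/125)] with pair-specific n, or √[MSE × 2/150] with the harmonic mean n = 3/(1/250 + 1/125 + 1/125) = 150. The SAP does not say which applies.
- Two-sided error = 2 × [1 − Φ(1.965 × SE used / true SE)]

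**Calibration.** With equal SDs in all three arms, pair n gives 4.9% by formula and 5.1% by simulation, the nominal level. Harmonic n gives 3.8% and 4.0%.

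**Placebo at the floor (s_p = 0, equal active SDs).**
- MSE = 373/497 = 0.751 of the active-arm variance, about 25% too small.
- √0.751 = 0.866, so the SE is about 13% too small.
- Pair n: effective critical value 1.965 × 0.866 = 1.70, error 8.9%.
- Harmonic n: √(2/150)/√(1/250 + 1/125) = 0.1155/0.1095 = 1.054; 1.70 × 1.054 = 1.79, error 7.3%.
- A simulation of the SNK step-down (200,000 runs) gave 8.9% and 7.3%.

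**Dependence on placebo spread, equal active SDs.**

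| Placebo SD / active SD | Pair n | Harmonic n |
|---|---|---|
| 0 | 8.9% | 7.3% |
| 0.2 | 8.7% | 7.1% |
| 0.4 | 8.1% | 6.6% |
| 0.6 | 7.2% | 5.8% |
| 0.8 | 6.1% | 4.8% |
| 1.0 | 4.9% | 3.8% |

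**Dependence on the low-dose SD, middle-dose SD 0.5.**

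| Low-dose SD | Placebo SD | Pair n | Harmonic n |
|---|---|---|---|
| 0.4 | 0 | 6.7% | 5.4% |
| 0.4 | 0.2 | 5.9% | 4.7% |
| 0.6 | 0 | 10.9% | 9.1% |
| 0.6 | 0.2 | 10.1% | 8.4% |

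**After the change.** A Welch test on the two active arms gave 5.0-5.1% in simulation for low/middle SD ratios of 0.8, 1 and 1.25. A pooled two-arm t-test gave 5.0% with equal SDs, but 3.5% and 6.8% at ratios 0.8 and 1.25, which favours the unequal-variance form.

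**Effect on an interval.** With log10 SD 0.5, the two-arm 95% half-width is 1.966 × 0.5 × √0.012 = 0.108, so the GMT ratio is multiplied or divided by 1.28. With the error term shrunk by a zero-variance placebo arm it would be 0.108 × 0.866 = 0.093, a factor of 1.24, which is too narrow.

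**The case against.** The strongest reply is that the size rests on SDs the SAP does not give. On the harmonic-n convention usual for SNK, the figure is 7.3% at most with equal active SDs. It is close to nominal if the low-dose arm is less variable than the middle-dose arm, or if placebo titres spread more than expected. All of this stands, and it is why the result is given as a range. What it does not supply is a reason for placebo to enter the error term at all.

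A second reply is that the trial's stated aim is broad, with no dose-superiority hypothesis, success criterion or dose-selection rule. No stated decision therefore turns on 5% against 7% or 9%. This also stands, and it lowers the severity.

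Third, the list of GMT summaries is open-ended, and section 9 refers to table shells that are not at hand. An interval for each arm's GMT may therefore be intended. That would still not be an interval for the ratio between doses.

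Some stronger readings are tempting but not supported:

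- **That 8.1 contradicts 8.7.** Section 8.1 says: "The rank sum test will be used for the data of unknown or non-normal distribution". But it sets out general options, and 8.7 then assigns ANOVA with SNK to titres and rank-sum to IFN-gamma. A specific section choosing among general options is ordinary drafting.
- **That the plan definitely compares arithmetic means.** The endpoints and summaries are geometric; the scale of the ANOVA is simply unstated. This is an ambiguity to close, not a proven wrong test.
- **That the Ad5 antibody analysis has the same fault.** SARS-CoV-2 seronegativity does not fix Ad5 titres, and the SAP stratifies them at 200, so the floor argument does not reach them.
- **That vaccine-versus-placebo findings are in doubt.** The calculation concerns middle versus low dose only.

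**Conclusion.** The point holds for the SARS-CoV-2 ELISA and neutralizing titres, for the middle-versus-low comparison. With placebo SD near zero, equal active-arm SDs and no true dose difference, the two-sided error is about 7.3% (harmonic n) or 8.9% (pair n) instead of 5%. With a low-dose SD of 0.4-0.6 against 0.5 in the middle-dose arm and placebo SD 0-0.2, the range is about 5-9% or 6-11%. With equal active SDs it falls to nominal or below as placebo SD approaches theirs. Independently of any SD, the SAP leaves the analysis scale unstated and provides no between-dose GMT ratio or interval. Nothing elsewhere in the SAP repairs either gap. This should be fixed; it is not a must-fix, because no dose-selection rule or success criterion depends on the test.

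**What to change.** In section 8.7, for SARS-CoV-2 ELISA and neutralizing titres only:

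1. State that titres are analysed on the log10 scale.
2. Compare middle with low dose using the two active arms only, by a Welch test or an unequal-variance linear model, and report the GMT ratio with its 95% CI.
3. Compare each dose with placebo by an unequal-variance or rank test.
4. Report a 95% CI for each GMT and GMI.

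The Ad5 antibody analysis can stay as it is. The cost is SAP wording and standard SAS code, with no change to conduct or sample size. The downside is that p-values for the dose comparison become slightly less favourable.
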